2.1 Overview of Study Design

A5372 is an open-label, non-randomized, two-arm, multicenter PK study to investigate the potential interactions between DTG and steady state RPT when RPT is prescribed with INH daily for 4 weeks (1HP) in HIV-1 and LTBI co-infected individuals.

The study regimen will be as follows, days 1 through 28.

Arm 1

- DTG 50 mg orally BID (~12 hours apart)
 - 1st dose: DTG 50 mg each morning from non-study ARV supply
 - 2nd dose: DTG 50 mg each evening from study supply
- 1HP: INH 300 mg + RPT 600 mg orally each morning for 4 weeks

Arm 2 (upon opening; contingent on assessment of DTG PK data from participants in Arm 1)

- DTG 50 mg orally each morning from non-study ARV supply
- 1HP: INH 300 mg + RPT 600 mg orally each morning for 4 weeks

All participants must also be on once-daily DTG-based ARV treatment with 2 NRTIs (excluding TAF) during the study. All participants must receive pyridoxine (vitamin B6) 25 or 50 mg with each dose of INH based on the current local, national, or international dosing guidelines.

Initially, the study will open with Arm 1. Once DTG concentrations data from the first 32 evaluable participants in Arm 1 are available, the core team will review the DTG PK data to ensure sufficient plasma exposures of DTG (C_{tau}) are achieved with twice-daily DTG dosing. This review will consist summarizing data completeness, participant evaluability for PK, and observed minimum concentrations. Provided: (1) there are 32 evaluable participants with minimum concentrations, (2) these minimum concentrations are above 158 ng/mL, and (3) there are no worrisome outliers among these minimum concentrations, the PK data will be used to model the anticipated PK of QD DTG when coadministered with 1HP. Based on these models and simulations of QD DTG dosing with 1HP, a decision will be made on whether to open Arm 2 for enrollment. Details on the criteria for opening Arm 2 are given in the protocol (Section 7.4) and herein (Section 4.5).

Plasma PK profiles for DTG will be determined at two time points. At the first time point, plasma samples will be drawn in participants at steady state with respect to DTG when receiving once daily DTG prior to 1HP. At the second time point, DTG will be given BID in Arm 1 and QD in Arm 2 during the 1HP LTBI regimen; PK sampling for DTG will occur on day 28 of the 1HP regimen.

In the final statistical analysis, inference will be based on geometric mean ratios for DTG PK parameters (with/without co-administered 1HP) where each participant serves as their own control (ie, within-subjects design).

In addition, sparse PK sampling will be performed on days 3, 14, and 21 of the 1HP regimen.

Leftover plasma from the DTG analysis will be used to determine RPT concentrations achieved from 1HP dosing to support exploratory study objectives.

A participant is considered *evaluable* (for PK) if they (a) have completed 28 daily doses RPT/INH within the 6-week study period, (b) have completed intensive PK sampling at both the day 0 and day 28 visits. Furthermore, each visit must have been conducted after 3 consecutive days of dosing, with at least 6 plasma samples collected and (for Arm 1) with both the 23- and 24-hour samples collected.

All participants must receive pyridoxine (vitamin B6) 25 or 50 mg with each dose of INH based on the current local, national, or international dosing guidelines.

Participants enrolling to A5372 will not be randomized. Enrollment will not be stratified.

2.2 Hypothesis

Dolutegravir (DTG) concentrations, when given twice daily (BID) or once daily (QD) with coadministration of 4 weeks daily rifapentine (RPT) (600 mg) and isoniazid (INH) (300 mg) [1HP], will maintain steady-state plasma trough DTG concentrations above 158 ng/mL in 95% of study participants. The value 158 ng/mL is the 5th percentile steady-state trough concentrations of DTG which has been demonstrated to be sufficient in maintaining virologic suppression.

2.3 Study Objectives

This Primary SAP addresses the following primary and secondary objectives listed in the study protocol. The remaining study objectives in the protocol will be addressed in subsequent analysis plans.

2.3.1 Primary Objectives

1. To determine the dosing for DTG that, when given together with 1HP, achieves target exposures (C_{trough}) of standard-dose DTG when it is given without RPT [Objective 1.2.1; this objective will be addressed by the study pharmacologists].
2. To estimate the steady-state plasma pharmacokinetic (PK) parameters of DTG when DTG 50mg is dosed twice daily (BID) with 1HP [Objective 1.2.2].
3. If Arm 2 opens, to estimate the steady-state plasma PK parameters of DTG when DTG 50 mg is dosed once daily (QD) with 1HP [Objective 1.2.3].

2.3.2 Secondary Objectives

1. To evaluate the safety of coadministration of DTG-based ART with 1HP [Objective 1.3.1].
2. To evaluate the tolerability of coadministration DTG-based ART with 1HP [Objective 1.3.2].

3. To estimate the proportion of participants who maintain virologic suppression when DTG-based ART is coadministered with 1HP [Objective 1.3.3].

2.4 Overview of Sample Size Considerations

Sample size estimates are based on the desired precision model-based estimates of DTG PK parameters in the presence and absence of 1HP. These models, once validated, will further be used to determine recommended DTG dosing algorithms for the treatment of patients living with HIV and co-infected with LTBI, pending appropriate safety assessment.

The sample size determination was done by evaluating different study designs (varying the numbers of participants and time points, assuming the design where each participant is its own control) using clinical trial simulations. See protocol version 1.0, Section 10.4 for details of clinical trial simulations.

The effect of RPT on DTG PK parameters (bioavailability) was assumed to be a decrease of 30%-50%. Inter-participant variability in PK parameters (CL and F) was assumed to be 25-40%. The time course of RPT induction was considered.

Under these assumptions, data from ≥ 32 participants in Arm 1 will provide $>80\%$ power to detect the hypothesized drug-drug interaction effect on bioavailability, and to unbiasedly (relative bias $<5\%$) and precisely (RSE $<25\%$) estimate PK parameters and inter-participant variability.

These estimated unbiased parameters will be then used for simulations of Arm 2 and derivation of the median 5th percentile of DTG troughs by simulations. The probability of opening Arm 2 will be dependent on magnitude of both the decrease in bioavailability due to drug-drug interactions and the between-participant variability. Precise estimate of drug-drug interaction coupled with acceptable between-participant variability will provide 90% chance of making a correct decision if Arm 2 opens.

The proposed design requires at least 32 evaluable participants, each of whom has intensive PK sampling conducted at both visits, conducted after 3 consecutive days of dosing recorded in participant diaries, the third of which is observed being taken in the clinical research site, with at least 6 plasma sample collections (per visit) which must include the 23- and 24-hr samples. Such data is expected to provide estimated pharmacokinetic parameters with required the precision, defined as relative standard errors $<10\%$ for typical values, and RSE $<25\%$ for random effects (between subject variability).

To protect against data loss after closure to accrual (e.g., lost specimens, assay problems), the study will enroll 36 participants in each arm. This is an increase of $\sim 12\%$ over the required sample size of 32 evaluable participants.

2.5 Overview of Interim Monitoring Reviews by the TB TSG Study Monitoring Committee (SMC): Reviews for Safety and Study Conduct

The SMC will provide independent oversight to safeguard the well-being of study participants and to ensure study integrity. Interim analyses of study progress and conduct as well as participant safety will be

reviewed by the SMC approximately every 6 months. The first interim review will occur no more than 6 months after the enrollment of the first study participant. (If accrual is rapid enough that only a short period of time – 1 month, say – would elapse between analyses for the SMC review and for the interim PK analysis for Arm 1 participants, the SMC review will not be conducted.) For all reviews, detailed information on safety (including treatment tolerability and mortality), and administrative aspects (including accrual, retention, compliance with study requirements) will be provided by study statisticians. The A5372 Study Progress, Data, and Safety Monitoring Plan (SPDSMP) provides details of the contents of reports to the SMC.

In the event that 3 or more participants experience Grade 3 or higher AEs deemed to be definitely, probably, or possibly related to DTG, RPT and/or INH, the study will be halted until an SMC review takes place. (“Related to” values will be assigned by the core team on regular calls or emails.)

An additional SMC review may also be convened if a concern is identified by the DAIDS clinical representative, study chairs, or study statisticians in consultation with the team.

To determine whether Arm 2 (QD dosing) will open to accrual, an interim analysis will be conducted by the study pharmacologist (see Section 4.5 herein). When this analysis has been completed, the team will inform the SMC of results and of the team’s decision.

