10.4 Sample Size and Accrual

Sample size estimates are aimed to provide data to support precise estimation of the pharmacokinetic model parameters for DTG in the presence and absence of 1HP. These models, once validated, will further be used to deliver dosing algorithms for DTG to be recommended for treatment of patients living with HIV and co-infected with LTBI, pending appropriate safety assessment.

The sample size assessment was done by evaluating different study designs (varying number of participants and time points) using clinical trial simulations. The stochastic simulation-estimation (SSE) methodology for clinical trial simulation and re-estimation was employed to evaluate sample sizes required to evaluate key pharmacokinetic parameters with precision adequate for decision making on use of RPT + DTG at the proposed doses. This methodology simulates the data from the planned trial with proposed design (number of samples, participants) followed by the estimation of the parameters under the true and alternative models. This is repeated at least 1000 times and parameter estimates relative standard errors and between subject variability (BSV) estimates are assessed. This methodology was used to assess sample size calculations and probability of opening Arm 2. The effect of RPT on DTG PK parameters

(bioavailability) was assumed to be 30%-50% decrease based on a previously developed model of DTG + 3HP [16]. The range of inter-participant variability in PK parameters (CL and F) was assumed to be 25-40%. The team has assumed design where each participant is its own control and time course of RPT induction is considered. Under these assumptions, data from ≥ 32 participants will provide $>80\%$ power to detect the DDI effect on bioavailability and to unbiasedly (relative bias $<5\%$) and precisely (RSE $<25\%$) estimate PK parameters and inter-participant variability. These unbiased parameters will be then used for simulations of Arm 2 and derivation of the median 5th percentile of DTG troughs by simulations. Probability of opening Arm 2 will be dependent on magnitude of both, decrease in bioavailability due to DDI and between participant variability. Decrease in bioavailability of up to 35% coupled with acceptable inter-participant variability (up to 30%) will provide 90% chance of satisfying criteria for opening Arm 2.

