4.6 Analysis of the Primary Objective 1 (Conducted by Study Pharmacologist)

In order to determine the dosing for DTG that, when given together with 1HP, achieves target exposures (C_{24}) of standard-dose DTG when it is given without RPT, the distribution of simulated DTG C_{24} values (based on concentrations from Arm 1 and develop population pharmacokinetic model) will be compared

with the historical data from SPRING Study (e.g., C_{tau} in the DTG 10 mg dosing arm) to examine whether dosing of DTG 50 mg BID will maintain above the trough concentration necessary for virologic suppression.

The same analysis will be conducted for Arm 2 if it opens. For this objective, a separate population PK analysis will be conducted (as described in Section 4.5.2).

There is no specific outcome measure associated with this analysis. The “outcome” is the characterization (through modeling) of the relationship between dosing (amounts, frequencies) and CIs around predicted C_{min} values; this analysis will be performed by the study pharmacologist.

4.7 Analysis of Primary Objectives 2 and 3 (outcome measures listed in Section 3.1; conducted by Study Pharmacologist)

For all PK parameters, the following descriptive statistics will be reported by arm and visit: mean, standard deviation, coefficient of variation, median, 5th and 95th percentiles, minimum, and maximum, as well as mean and standard deviation on the natural log (base e) scale. This analysis is conducted using the primary PK analysis population. To assess the overall effect of 1HP on DTG PK parameters, geometric mean ratios (GMRs) and associated 90% CIs will be calculated by arm. The ratio is with (after initiation of 1HP; numerator) vs without (before initiation of 1HP; denominator) co-administered 1HP. The DTG PK parameters are C_{min} , C_{max} , and total daily exposure as measured by AUC_{0-24h} . (For Arm 1, day 28 (BID dosing), participant-specific AUC_{0-24h} will be estimated by combining (summing) areas for the two BID dosing intervals. For Arm 1 day 0, and for Arm 2 days 0 and 28 (QD dosing), participant-specific AUC_{0-24h} values will be estimated from concentrations collected over the single 24-hour dosing interval.)

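### In Arm 1 the Day 28/Day 0 AUC ratio mixes the 1HP effect with a doubled daily DTG dose, and no dose-adjusted interaction estimate is listed among the results

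*SAP*

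**What the plan says.** **Sizing.** SAP 2.4 opens with "Sample size estimates are based on the desired precision model-based estimates of DTG PK parameters in the presence and absence of 1HP". Protocol 10.4 gives the method: a simulation-estimation "methodology for clinical trial simulation and re-estimation was employed to evaluate sample sizes required to evaluate key pharmacokinetic parameters". The effect of RPT on DTG bioavailability "was assumed to be a decrease of 30%-50" per cent, with 25-40% variability between participants in CL and F. Both documents then claim >80% power for that effect: "power to detect the hypothesized drug-drug interaction effect on bioavailability" in SAP 2.4 and "power to detect the DDI effect on bioavailability" in protocol 10.4. The number needed is 32: "The proposed design requires at least 32 evaluable participants".

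**Inference.** SAP 2.1 says that in the final analysis "inference will be based on geometric mean ratios for DTG PK parameters (with/without co-administered 1HP"). SAP 4.7 uses these ratios, with 90% CIs, to judge the effect of 1HP on C_min, C_max and AUC0-24h. In Arm 1 the Day 28 AUC0-24h is obtained "by combining (summing) areas for the two BID dosing intervals", while Day 0 covers one once-daily interval. SAP 4.8.2 states the two conditions openly: BID DTG with 1HP over QD DTG alone. No dose adjustment is mentioned.

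**Reading rule.** SAP 6.3 treats a ratio near 100% as no effect of the co-administered drug. It treats one significantly below 100% as induced metabolism, and one significantly above as reduced metabolism and higher exposure.

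**Results listed.** SAP 3.1, 4.7, 4.8.2 and 5.8 contain C_max, C_min and AUC0-24h and their ratios. None lists a relative bioavailability or a per-dose ratio, and 4.8 plans no sensitivity or supplementary analyses.

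**The concern.** Between Day 0 and Day 28 an Arm 1 participant changes in two ways: 1HP is added and the daily DTG dose goes from 50 mg to 100 mg. The ratio responds to both. For AUC0-24h the two changes pull in opposite directions, and over the range of interaction assumed in SAP 2.4 the doubled dose offsets the loss of bioavailability or outweighs it.

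The ratio is nevertheless introduced as a measure of the 1HP effect and comes with a general rule for reading it. A reader of the primary report who applies that rule to the Arm 1 AUC row would draw a wrong conclusion about the interaction. The quantity that would correct this reading, the bioavailability effect for which the arm was sized, is not in the listed results.

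**Working it through.** **1. The plan's own figure.** The >80% cannot be reproduced exactly. The model structure, residual error, within-participant variability and test are not given, and the figure is a lower bound. As a proxy, take a paired t-test on the log scale with n = 32 and effect ln(1 - d), where d is the fall in bioavailability. The SD of the log difference is an assumption:

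- A 25-40% CV corresponds to sqrt(ln(1 + CV²)) = 0.246 to 0.385.
- Two independent occasions multiply this by sqrt(2), giving 0.348 to 0.545.
- With CL and F both independent on both occasions the factor is 2, giving 0.492 to 0.771.

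With a two-sided 5% test and SD up to 0.545, power is 95-100%. In the worst corner (SD 0.771, d = 30%) it is 72%, or 82% with a one-sided 5% test. The printed >80% is therefore plausible for the effect it names.

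**2. Expected Arm 1 AUC ratio.** If AUC is proportional to dose × F, and F is all that changes, as in the sizing:

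GMR = (2 × 50 mg × F(1 - d)) / (50 mg × F) = 2(1 - d)

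- d = 30%: 1.40
- d = 40%: 1.20
- d = 45%: 1.10
- d = 50%: 1.00

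**3. Where the 90% CI would fall.** Use the noncentral t with n = 32, df = 31, critical value 1.696 and noncentrality ln(2(1 - d)) × sqrt(32) / SD. The SD is assumed to be 0.3-0.6. The per-dose row uses ln(1 - d) instead.

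| Event | SD | d = 30% | 40% | 45% | 50% |
|---|---|---|---|---|---|
| CI wholly below 100%, as written | 0.3 | <0.01% | <0.01% | 0.03% | 5% |
| | 0.6 | <0.01% | 0.04% | 0.6% | 5% |
| CI wholly above 100%, as written | 0.3 | 100% | 96% | 55% | 5% |
| | 0.6 | 93% | 51.5% | 22% | 5% |
| CI wholly below 100%, per 50 mg dose | 0.3 | 100% | 100% | 100% | 100% |
| | 0.6 | 95% | 99.9% | 100% | 100% |

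For example, with d = 30% and SD 0.6, ln(1.40) = 0.336 and the noncentrality is 0.336 × 5.657 / 0.6 = 3.17. At d = 50% the true ratio is exactly 1, so 5% is simply the one-sided error rate.

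Over the wider SD range 0.246-0.771, the chance that the CI lies below 100% is at most 0.2% at d = 40%, at most 1% at 45%, and 5% at 50%. Per dose it is 82-100% throughout.

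**4. What a halving would look like.** The CI half-width on the log scale is 1.696 × SD / 5.657, which is 0.090 at SD 0.3 and 0.180 at SD 0.6. Around an expected ratio of 1.00, a typical 90% CI is therefore 0.91-1.09 or 0.84-1.20. By SAP 6.3 that is a result of no effect.

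**5. The other two parameters.** Under a one-compartment steady-state model with assumed half-life 6-24 h, absorption rate 0.5-2 per hour and only F changing:

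- The trough ratio is 1.21-3.50 over d = 30-50%, so it too points upwards.
- The C_max ratio is 0.63-0.88 at d = 50%, with a 36-100% chance that the CI lies below 100% for SD 0.246-0.545. At d = 30% it is 0.89-1.23, with a chance of 0-85%.

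C_max can therefore show a reduction where AUC0-24h does not.

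**The case against.** A reader might infer that the >80% power is false, or that it collapses to 0-5%. The documents do not support this. SAP 2.4 and protocol 10.4 tie the figure to a model-based bioavailability effect, never to a GMR, so setting >80% beside 0-5% compares two different quantities.

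A reader might also infer that a planned test would fail. None is planned: SAP 4.3 puts the emphasis on estimation, and no test that the ratio is below 1 is defined. The probabilities above describe where the interval would lie. Nor does 0-5% apply to every ratio in the SAP, as C_max shows.

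The strongest counter-argument is that Objective 2 is to estimate DTG PK under BID dosing with 1HP, and 4.8.2 defines the contrast openly. As a comparison of regimens, a ratio at or above 1 is informative and not in a wrong direction. Moreover, the population PK model has not been abandoned. It supplies the PK parameters (4.4), the Arm 2 decision (4.5.2) and Objective 1 (4.6), and the joint RPT-DTG interaction model is an Other outcome in protocol 10.2.3, outside the primary report.

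All of this stands, and it limits the point. It does not remove it. SAP 4.7 still presents the Arm 1 ratio as an assessment of 1HP, and 6.3 still supplies a rule that misreads it. The 6.3 text is general, but nothing in the SAP exempts Arm 1.

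**Conclusion.** The point holds for the Arm 1 AUC0-24h ratio. Over the 30-50% fall in bioavailability assumed in SAP 2.4, the expected value is 1.40 to 1.00, and the 90% CI lies below 100% with probability 0-5%. Under SAP 6.3 a halving would read as no effect and a 30% fall as increased exposure. The bioavailability effect that the >80% describes is missing from the listed results, although the figure itself is plausible.

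The ratio of 2(1 - d) rests on AUC being proportional to dose × F, with F alone affected. The probabilities also rest on an assumed log-difference SD of 0.3-0.6, since the documents give no within-participant SD, but the conclusion is the same over 0.246-0.771. Arm 2 is unaffected because it compares QD with QD. The defect lies in what is reported and how it is read, not in the sample size.

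**What to change.** 1. In SAP 3.1, 4.7 and 5.8 add for Arm 1 the AUC0-24h GMR per 50 mg dose (Day 28 value divided by 2), or the model-estimated relative bioavailability of DTG with versus without 1HP and its 95% CI, or both.
2. In 4.7 and 5.8 state that the undivided Arm 1 GMR compares regimens (BID with 1HP versus QD alone), and that the 6.3 rule for values near 100% does not apply to it.
3. In 2.4 add a sentence that the >80% refers to the model parameter and not to this GMR.

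The cost is SAP wording and one or two rows in a results table, using data and a model already planned, with no new participants or samples. There is a small downside: the bioavailability estimate depends on the model, and the per-dose ratio assumes dose-proportional AUC. Reporting both would show how much that matters.

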There are less data when DTG is given with RPT as compared to rifampin. In a small study assessing the PK and safety of DTG when given at a dose of 50 mg once-daily together with once-weekly INH and RPT (each dosed at 900 mg, 3HP) in HIV-uninfected healthy volunteers, DTG trough (C_{12}) concentrations were reduced by 43%, 74%, and 53% 2, 3, and 6 days after the dose, respectively, compared to when DTG was given alone [10]. The lowest average C_{12} , though, remained 5.3 times higher than the protein-adjusted IC_{90} for DTG, suggesting that even with these reductions in exposure, virologic suppression was likely to be maintained in individuals with HIV taking standard-dose DTG. The combination, however, was poorly-tolerated, with flu-like syndrome seen in two of three volunteers. Brisk immune responses have been seen in healthy volunteers given rifamycins previously [6, 11-13] and in individuals with TB. Rifamycin hypersensitivity is most common when rifamycins are dosed intermittently [14, 15].

In a similar study of 3HP in HIV/latent TB infection (LTBI) co-infected individuals, Dooley and colleagues conducted PK sampling of patients receiving 50 mg DTG in combination with once weekly RPT and INH. The geometric mean (GM) trough concentration of DTG pre-HP treatment was 1003 ug/mL (5th-95th percentile: 500-2080), and during HP treatment 546 (134-1616) with all trough concentrations except for one above the DTG IC_{90} of 64 ug/mL. Overall, although weekly HP decreased DTG bioavailability, which was associated with a modest decrease in trough concentrations, all trough concentration except for one were above the DTG IC_{90} , and DTG clearance remained unchanged after the 8th weekly dose of RPT/INH. Notably, with regard to safety, co-administration of DTG and weekly HP was well-tolerated, with no HP-related Grade >3 AEs. All viral loads were suppressed [16]. These data, combined with the week 48 results of the INSPIRING study [7] add to the evidence in that safety events such as those seen in the Brooks et al. study [10] present differently in healthy volunteers versus HIV/LTBI co-infected individuals.

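### SAP 2.4 gives 90% as the chance of a correct decision if Arm 2 opens, but protocol 10.4 gives 90% as the chance of meeting the opening criterion under stated limits

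*SAP*

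**What the plan says.** Protocol 10.4 describes simulation-estimation work, run at least 1000 times, that was used for the sample size and for the probability of opening Arm 2. The fall in bioavailability "was assumed to be 30%-50% decrease based on a previously developed model of DTG + 3HP". On variability: "The range of inter-participant variability in PK parameters (CL and F) was assumed to be 25-40" (per cent). The result for Arm 2 carries a condition, "Decrease in bioavailability of up to 35% coupled with acceptable inter-participant variability (up to 30" (per cent), and under that condition the design "will provide 90% chance of satisfying criteria for opening Arm 2".

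SAP 2.4 summarises the same work in a parallel paragraph, refers to section 10.4 of protocol version 1.0 for the simulations, and repeats the 30-50% and 25-40% ranges. It agrees on what drives the result: "The probability of opening Arm 2 will be dependent on magnitude of both the decrease in bioavailability" and the between-participant variability. Its next sentence changes both parts of the protocol's statement. The condition becomes "Precise estimate of drug-drug interaction coupled with acceptable between-participant variability", and this "will provide 90% chance of making a correct decision if Arm 2 opens".

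The rule is in SAP 4.5.2 and protocol 7.4. Arm 1 data from at least 32 evaluable participants feed a population PK model, once-daily dosing is simulated 1000 times, and the model-based criterion is met if the median of the simulated 5th percentiles of the trough is not below 158 ng/mL.

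**The concern.** The two sentences carry the same figure but are not the same probability. The protocol's runs from an assumed truth to the event of opening. The SAP's runs from the event of opening back to whether opening was right. The second depends on how often the rule opens Arm 2 when the true once-daily 5th percentile is below 158 ng/mL, and neither document reports that.

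This is the stated operating characteristic of the trial's one gating decision, and it has the same standing as a stated power. Under SAP 2.6 and 4.5 the core team takes the decision and the SMC is notified of it. Someone reading the SAP alone would conclude that the risk of opening Arm 2 wrongly had been shown to be 10%. The supplied documents do not show that.

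**Working it through.** **1. The two statements in symbols.** Let d be the fall in bioavailability and v the inter-participant variability.

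- Protocol 10.4: P(criterion met | d ≤ 35%, v ≤ 30%) = 0.90.
- SAP 2.4: P(decision correct | Arm 2 opens) = 0.90, given a precise interaction estimate and acceptable variability, with no numeric limit on either.

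**2. Can the 90% be reproduced?** No. It comes from a population PK simulation whose clearance, volume, absorption, induction and residual-error values are not in the documents. The point is therefore about what the figure measures, not its value.

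**3. What the SAP's quantity would need.** Let p be the chance that the true 5th percentile is at least 158 ng/mL, and x the average chance of opening when it is not. Suppose also that 0.90 applied to every adequate truth, which goes further than the protocol does. Bayes' rule gives

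P(correct | opens) = 0.90p / [0.90p + x(1 − p)].

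Setting this to 0.90 gives 0.90p + x(1 − p) = p, so x = 0.10p/(1 − p). It holds for p = 0.5 with x = 0.10, for example, and fails for other pairs. Neither p nor x is in the documents, so 0.90 cannot be derived.

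**4. Within one fixed scenario.** If the true 5th percentile is at least 158 ng/mL, a decision to open is correct with probability 1. If it is below, the probability is 0. Neither is 0.90, so the SAP's figure needs a weighting over scenarios.

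**5. Does precision supply it?** The model-based rule compares a point summary with 158 ng/mL and has no margin. If the truth is at 158, a roughly unbiased estimate falls on either side about equally often. A simplified stand-in illustrates this. It assumes lognormal troughs, n = 32, 20,000 replicates, and opening when the estimated 5th percentile is at least 158. The log-scale SD is ln(2080/500)/(2 × 1.645) = 0.43, from the pre-treatment 5th-95th percentile range of the weekly-regimen cohort in protocol 2.1.1. Only the ratio is used, so the printed units do not matter.

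| True 5th percentile (ng/mL) | P(criterion met) |
|---|---|
| 130 | 0.05 |
| 150 | 0.35 |
| 158 | 0.52 |
| 175 | 0.82 |
| 195 | 0.97 |

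The stand-in is not the trial's model. At a 35% fall from that cohort's baseline (1003, read as ng/mL) it gives about 100%, not 90%. It shows only how the rule behaves near the threshold.

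**6. How much the missing limits matter.** Bioavailability: (35 − 30)/(50 − 30) = 5/20, a quarter of the assumed range. Variability: (30 − 25)/(40 − 25) = 5/15, a third. Without the limits, the SAP sentence can be read as covering the whole of both ranges.

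**The case against.** **It may be loose drafting.** In the favourable scenario opening is the right decision, so the chance of deciding correctly there equals the chance of opening, 90%. That may be what was meant. It does not rescue the text, which conditions on Arm 2 opening and does not state the scenario.

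**The SAP keeps a condition on each factor.** This stands in part. Variability is still called acceptable, but without a figure. For the interaction, the condition has moved from its size to the precision of its estimate, and that is a different condition.

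**The SAP cites protocol version 1.0, which was not supplied.** The sentence may have been carried over from it, and a false-opening rate may have been simulated but not reported. So the supportable claim is that the SAP's figure is a different quantity from the one in the supplied protocol and has no support in the supplied text. Since SAP 1.2 declares the SAP to be for protocol version 2.0, the mismatch still needs correcting.

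**The sentence feeds no rule.** This stands, and it limits the consequence.

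**Two stronger readings are tempting, and the documents support neither.** A reader might put a number on the true chance of a correct decision by choosing values for p and x. Any such range reflects only the values chosen. A reader might also take the weekly-regimen cohort in protocol 2.1.1, whose trough geometric mean fell and whose on-treatment 5th percentile is given as 134, as showing that the favourable scenario is already ruled out. That would equate a fall in trough with a fall in bioavailability. The text on that cohort gives no variability in CL and F, the regimen was weekly 900 mg, and protocol 2.1.1 says the effect of rifapentine dose and frequency is still to be studied.

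**Conclusion.** The point holds as a misstated operating characteristic and an inconsistency between the two documents. The SAP's 90% is not the protocol's 90%: the conditioning is reversed, the 35% and 30% limits are gone, and precision has replaced size of effect. Its stated chance of a correct decision is unsupported, because neither a false-opening rate nor a weighting over scenarios is given.

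The true chance of a correct decision cannot be computed from the documents, and it has not been shown to be lower than 90%. The statement that the model-based criterion is met about half the time at the threshold assumes an estimate that is roughly unbiased with a roughly symmetric error. The stand-in figure of 0.52 agrees with it but does not reproduce the trial's model. A reader might infer that the opening rule is itself faulty or that participants' exposure changes. Neither follows, because SAP 4.5 and protocol 7.4 do not use this sentence.

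**What to change.** Replace the SAP 2.4 sentence with the protocol's probability and its limits, for example: *If bioavailability falls by no more than 35% and inter-participant variability is no more than 30%, the chance of satisfying the Arm 2 opening criterion is about 90%.*

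Remove the claim about a correct decision, unless the SAP also reports the simulated probability of opening Arm 2 when the true once-daily 5th percentile is below 158 ng/mL. If it does, give that probability for several true values on each side of the threshold. Point the SAP's cross-reference at the protocol version the SAP is written for, or confirm that version 1.0 says the same.

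The cost is one sentence and one cross-reference. The design, sample size and opening rule stay as they are. The stated figure will read less favourably, because its limits become visible. Reporting false opening as well would take extra output from the existing simulation set-up, or a further run if no scenario below the threshold was simulated.
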